6.5. Day 28 Follow up Assessment (\pm 5 Days)

The following evaluations are to be completed if this visit is conducted in person. For participants who have been discharged from hospital, the final evaluation can be made by phone. Only AE and concomitant medication and ordinal scale (if discharged on or after Day 14) review are to be completed if visit is conducted by phone.

- Physical examination and vital signs (heart rate, temperature, blood pressure)
- Documentation of respiratory status:

Respiratory rate

— Oxygen supplementation: room air, low flow O₂ (L/min and %), high flow O₂ (L/min and %), CPAP/BIPAP (FiO₂ or %), mechanical ventilation (FiO₂ or %), ECMO

Oxygenation: SpO₂ or PaO₂

Radiographic findings (if available)

- Review AEs and document concomitant medications
- Review the Ordinal Scale (Section 6.9). If subject was not discharged by Day 14, any change in category and the date of any change in category from Day 14 to discharge (or Day 28) should be recorded

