Appendix 2. Study Procedures Table

	Screening	Baseline / Day 1 ^b	Day 2	Day 3	Day 4	Day 5	Days 6 and 7	Day 8	Day 9	Day 10	Days 11, 12 and 13	Day 14	Day 28 ^c Follow-up (± 5 days)
Written Informed Consent	X												
Medical History	X												
Physical Examination	X	X	X	X	X	X	X	X	X	X	X	X	X
Height	X												
Vital Signs ^d	X	X	X	X	X	X	X	X	X	X	X	X	X
Study Laboratory Testing	X	X		X		X		X		X		X	
Respiratory Status	X	X	X	X	X	X	X	X	X	X	X	X	X
Ordinal Scale		X	X	X	X	X	X	X	X	X	X	X	X
Pregnancy Test	X												
CCI													
Virologic Testing ^e		X		X		X		X		X		X	
RDV Dosing for Group 1		X	X	X	X	X							
RDV Dosing for Group 2		X	X	X	X	X	X	X	X	X			
Adverse Events	X	X	X	X	X	X	X	X	X	X	X	X	X
Concomitant Medications	X	X	X	X	X	X	X	X	X	X	X	X	X

- a Includes heart rate, respiratory rate, temperature, blood pressure, SpO₂, and body weight. Body weight collected on Screening and Day 1 and otherwise if available.
- b Assessments need not be repeated if performed within 24 hours of screening procedures; data collection other than adverse events and concomitant medications should stop at Day 14 or discharge, whichever is earlier.
- c Day 28 evaluations completed if the visit is conducted in person. Only adverse event and concomitant medications review completed if visit conducted by phone.
- d [REDACTED]
- e Virologic (SARS CoV 2) testing for subjects/sites participating in this portion of the study on Days 1, 3, 5, 8, 10, and 14.

Appendix 3. Pregnancy Precautions, Definition for Female of Childbearing Potential, and Contraceptive Requirements

1) Definitions

a. Definition of Childbearing Potential

For the purposes of this study, a female born subject is considered of childbearing potential following the initiation of puberty (Tanner stage 2) until becoming post-menopausal, unless permanently sterile or with medically documented ovarian failure. No documentation of Tanner stage will be required for people unless deemed prepubescent.

Women are considered to be in a postmenopausal state when they are ≥ 54 years of age with cessation of previously occurring menses for ≥ 12 months without an alternative cause. In addition, women of any age with amenorrhea of ≥ 12 months may also be considered postmenopausal if their follicle stimulating hormone (FSH) level is in the postmenopausal range and they are not using hormonal contraception or hormonal replacement therapy.

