3.8.2. Analysis Visit Windows

Participant visits might not occur on protocol-specified days. Therefore, for the purposes of analysis, observations will be assigned to analysis windows. The study day as defined in Section 3.8.1 will be used when data are summarized by visit.

Vital signs were to be collected daily; therefore, windows are not assigned and results will be summarized for each Study Day, except for Study Day 28. For Study Day 28, the nominal day is Study Day 28, the lower limit is Study Day 15 and there is no upper limit.

Ordinal scale results were to be recorded prior to dosing on Study Day 1. The worst result for each day from Day 1 (after first dose) through the earliest of discharge date or Day 14 was to be recorded. For participants who were discharged after Day 14, changes in score category were to be recorded each day from Day 15 to the earliest of discharge date or Day 28. For the ordinal scale, baseline is defined as the value recorded prior to dosing, or the last value obtained prior to the first dose date if the predose value was not recorded on the day of dosing. Results will be summarized for each Study Day without windows. If more than one result was reported on the same day, the worst result will be selected.

The analysis windows for hematology and chemistry laboratory parameters are presented in Table 3-1.

Table 3-1. Analysis Windows for Hematology and Chemistry Laboratory Tests (hemoglobin, hematocrit, platelet count, WBC, ALT, AST, total bilirubin, glucose, serum creatinine, and creatinine clearance)

Visit ID	Nominal Day	Lower Limit	Upper Limit	
Baseline/Day 1	1		1 (predose)*	
Day 3	3	1 (postdose)*	3	
Day 5	5	4	6	
Day 8	8	7	8	
Day 10	10	9	11	
Day 14	14	12	15	
Post Day 14**	28	16		

^{*} For Baseline, the upper limit includes values collected at or prior to the first dose date/time. For Day 3, the lower limit includes values collected after the first dose date/time on Day 1.

3.8.3. Selection of Data in the Event of Multiple Records for an Analysis Visit Day

Depending on the statistical analysis method, single values may be required for each Study Day/ analysis window. For example, change from baseline by visit usually requires a single value, whereas a time-to-event analysis does not require 1 value per Study Day or analysis window.

If multiple valid, nonmissing measurements exist for a Study Day/analysis window, records will be chosen based on the following rules if a single value is needed:

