6.2. Efficacy Endpoints of Interest

Efficacy endpoints of interest include endpoints based on clinical status assessed by a 7-point ordinal scale. The endpoint will be derived by combining the available death, hospital discharge alive and ordinal scale assessment reported by the site, where death supersedes discharge alive and discharge alive supersedes the ordinal scale score reported by the site. The proportion of participants for each ordinal scale category is expressed as percentages for presentation purpose.

Sites were instructed to report the worst ordinal scale category for each day. Therefore, the ordinal scale result on the day the participant was discharged alive does not necessarily reflect Not hospitalized (7). The definition of clinical status based on the 7-point ordinal scale is defined as follows:

- If a participant dies while hospitalized (as recorded on the Death eCRF and Hospitalization eCRF), the endpoint on the day of death and all subsequent days through Day 28 will be set to Death (1)
- If the participant is discharged alive, the endpoint on the day of discharge alive and all subsequent days through Day 28 will be set to Not hospitalized (7)
- If the participant is discharged alive and dies on the same day or a later day (as recorded on the Death eCRF and Hospitalization eCRF), the endpoint on the day of discharge alive and all subsequent days until the day of death will be set to Not hospitalized (7). On the day of death and all subsequent days through Day 28, the endpoint will be set to Death (1),

Every effort will be made to obtain clinical status data for all participants prior to discharge alive. The last known clinical status will be used for days with missing clinical status (eg, where the reason for Hospital Discharge is not "Discharged Alive" and the participant has not died). All post-baseline days with missing ordinal scale score, from Day 2 to Day 14 and Day 28, will use the previous last known clinical status.

Efficacy endpoints of interest include

- Clinical status on Days 1 to 14, Day 28 and last available assessment
- Change in clinical status on Days 5, 7, 11, 14, 28, and last available assessment
- Time to clinical improvement (days): Clinical improvement is defined as a ≥ 2-point improvement from baseline clinical status or discharged alive on the 7-point ordinal scale using the definition specified above.

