6.2.1. Analysis of Efficacy Endpoints of Interest

The number and percentage of participants in each clinical status category for each day from Baseline through Day 14 and at Day 28 and using the last available assessment will be summarized. These results will be summarized using (1) the clinical status definition in Section 6.2 and (2) with the definition specified in Section 6.2 but excluding days with missing ordinal scale score not due to death or discharge alive. In addition, stacked bar charts by study day (Baseline through Day 14 and at Day 28) will be produced using the definition specified in Section 6.2.

The number and percentage of participants in each clinical status category for each day from Baseline through Day 14 and at Day 28 and last available assessment will be summarized within each subgroup defined in Section 3.4.1.

The change from baseline in clinical status category on Days 5, 7, 11, 14, 28 and last available assessment will be summarized by group using descriptive statistics.

Number of days of oxygen support status modes (invasive mechanical ventilation, high flow oxygen, low flow oxygen) will be calculated as the number of days oxygen support was reported on the 7-point ordinal scale eCRF through death, discharge alive, or Day 14 and presented using descriptive statistics.

A shift table of baseline oxygen support status (death, invasive mechanical ventilation, high flow oxygen, low flow oxygen, room air, discharge alive) to Days 5, 7, 11, 14, 28 and the last available status will be included.

Duration of hospitalization will be calculated only for participants who are discharged alive on or prior to Days 11 and 28 and will be summarized using descriptive statistics.

All-cause mortality will be estimated using the Kaplan-Meier product limit method with all available data. Participants who did not die will be censored at the last study day.

Days to clinical improvement and days to recovery will be estimated using a competing risk analysis approach, with death as the competing risk. Participants without the endpoint being analyzed will be censored on the day of the last non-missing ordinal scale assessment.

Forest plots by subgroup will be presented for cumulative incidence of recovery on Day 28.

The number and percent of participants with \geq 1-point improvement, \geq 2-point improvement, and recovery will be presented with 95% confidence intervals on Day 5, Day 7, Day 11, Day 14, Day 28 and last available assessment.

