Hematology	Hematocrit (%)	1
Hematology	Platelet count (x10^9/L)	0
Hematology	WBC (x10^9/L)	2
Chemistry	ALT (U/L)	0
Chemistry	AST (U/L)	0
Chemistry	Total bilirubin (mg/dL)	2
Chemistry	Glucose (mg/dL)	0
Chemistry	Serum creatinine (mg/dL)	2
Chemistry	Creatinine Clearance by Cockcroft- Gault (mL/min)	1

Standard deviation and standard error will be reported to one more significant decimal place than the raw measurement.

Mean, median, minimum, Q1, Q3, and maximum will be reported to the same number of decimal places of the raw measurements.

Exceptions may be considered; for example, if more than 4 significant digits are provided for the measurement.

- 14) Last dose date is not expected to be missing. However, if last dose date is missing, it will be imputed using the maximum of non-missing, non-zero dose, study drug start and stop dates.
- 15) Ordinal scale and oxygen support status

The oxygen support status is derived from the ordinal scale:

Ord	linal Scale	Oxygen Support Status
1	Death	Death
2	Hospitalized, on invasive mechanical ventilation or ECMO	Invasive Mechanical Ventilation
3 Hospitalized, on non invasive ventilation or high flow oxygen devices High Flow Oxygen		
4 Hospitalized, requiring low flow supplemental oxygen Low Flow Oxygen		Low Flow Oxygen
5 Hospitalized, not requiring supplemental oxygen requiring ongoing medical care (COVID 19 related or otherwise) Room Air		Room Air
6 Hospitalized, not requiring supplemental oxygen no longer requires ongoing medical care (other than per protocol RDV administration) Room Air		Room Air
7	Not hospitalized	Discharge

16) Censoring rules

Time to death: participants are censored at the last known date alive (last study day)

Time to \geq 2-point improvement, time to \geq 1-point improvement, time to recovery; if a participant does not experience the event of interest and does not die, the participant is censored at the last non-missing ordinal scale assessment date.

17) Graded Laboratory Abnormalities Summary

The following labels will be used for laboratory abnormalities and Grade 3 or 4 laboratory abnormalities summary tables and listings:

Battery	Lab Test Label Used in I-labtox Listing	Toxicity Direction	Lab Test Label Used in t-labtox Table
	Hemoglobin	Decrease	Hemoglobin (Decreased)
Hematology	Platelets	Decrease	Platelets (Decreased)
	WBC	Decrease	WBC (Decreased)
	ALT	Increase	ALT (Increased)
	AST	Increase	AST (Increased)
	Creatinine	Increase	Creatinine (Increased)

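### Where an unrecovered inpatient has no Day 28 ordinal score, the SAP's censoring rule may inflate the Part B Day 28 cumulative incidence of recovery and improvement

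*SAP*

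**What the plan says.** **Censoring.** For the competing-risk analyses, SAP 6.2.1 says: "Participants without the endpoint being analyzed will be censored on the day of the last non-missing ordinal scale assessment". Appendix 2 item 16 applies the same rule to recovery and to both improvement endpoints, and ties it to a date: "the participant is censored at the last non-missing ordinal scale assessment date". Time to death is handled differently. Survivors are censored at the last study day.

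**Recording to Day 14.** SAP 3.8.2 calls for a daily score: "The worst result for each day from Day 1 (after first dose) through the earliest of discharge date or Day 14".

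**Recording after Day 14.** For participants discharged after Day 14, SAP 3.8.2 says "changes in score category were to be recorded each day from Day 15 to the earliest of discharge date or Day 28". For participants still in hospital at that point, protocol 6.5 says: "any change in category and the date of any change in category from Day 14 to discharge (or Day 28) should be recorded". Protocol 6.5 also lists an ordinal scale review at the Day 28 (± 5 days) visit, and the procedures tables in protocol Appendix 2 and SAP Appendix 1 both mark the scale at Day 28. A footnote to the protocol table nevertheless says "data collection other than adverse events and concomitant medications should stop at Day 14 or discharge, whichever is earlier", and the SAP table carries the same instruction.

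**Missing scores.** For clinical status, SAP 6.2 says: "All post-baseline days with missing ordinal scale score, from Day 2 to Day 14 and Day 28, will use the previous last known clinical status". It does not say whether a status filled in this way counts as non-missing when the censoring date is set.

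**The concern.** Consider an inpatient at score 4 on Day 14 who is still at score 4 on Day 28. If the only later entries are changes of category, this participant's last score is dated Day 14. The SAP then treats the participant in two ways. In the Day 28 status tables and percentages the participant counts as unrecovered, by carry-forward. In the time-to-recovery analysis the participant leaves the risk set at Day 14.

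A participant who improves after Day 14 normally leaves a dated change of category or a discharge date, and a death has its own record. Staying in the risk set then depends on having an event, so the censoring is informative and favours recovery. The outputs exposed are the competing-risk estimates of recovery and improvement, and the subgroup forest plots of Day 28 recovery. The distortion grows with the share of long stays. Subgroups that differ in that share could appear closer together, or otherwise differently placed, than they are.

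**Working it through.** The plan states no figure for this analysis, so there is none to reproduce. The documents give no recovery rates for Part B and no count of missing Day 28 scores. All rates below are assumptions.

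**Formula.** As shares of the cohort, let R14 = recovered by Day 14 and U = alive and unrecovered after Day 14. During Days 15 to 28, of U, r recover, d die and w remain unrecovered (U = r + d + w). Let f be the share of w with a score dated Day 28; the rest are censored at Day 14. The cumulative incidence estimate at Day 28 is

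CIF28 = R14 + U × r / (r + d + f × w).

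The true value is R14 + r, which the formula gives at f = 1.

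**Illustration A.** R14 = 0.85, r = 0.05, d = 0.01, w = 0.09, U = 0.15.
- f = 1: 0.85 + 0.15 × 0.05/0.150 = 90.0% (true value)
- f = 0.5: 0.85 + 0.15 × 0.05/0.105 = 92.1%
- f = 0: 0.85 + 0.15 × 0.05/0.060 = 97.5%

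**Illustration B, a sicker subgroup.** R14 = 0.60, r = 0.12, d = 0.04, w = 0.24, U = 0.40.
- f = 1: 0.60 + 0.40 × 0.12/0.40 = 72.0% (true value)
- f = 0.5: 0.60 + 0.40 × 0.12/0.28 = 77.1%
- f = 0: 0.60 + 0.40 × 0.12/0.16 = 90.0%

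**Wider grid.** A day-level competing-risk (Aalen-Johansen) calculation was run for 1000 participants, the approximate Part B size in SAP 1.2. It assumed 1% dead by Day 14; U of 5%, 10%, 20% or 30%; and, of U, 30%, 50% or 70% recovering and 5% dying in Days 15 to 28.

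| Unrecovered inpatients with no score after Day 14 | Inflation over the grid (percentage points) | Estimate at U = 10%, half recovering later (true 94.0%) |
|---|---|---|
| none | 0 | 94.0% |
| 25% | 0.2 to 1.9 | 94.6% |
| 50% | 0.5 to 4.4 | 95.4% |
| all | 1.2 to 16.7 | 98.1% |

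The largest case is a true 78.0% estimated at 94.7%. With every later recovery and death dated, as assumed here, the bias is never downward.

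**Visit window.** SAP 3.8.2 summarizes ordinal scores by study day without windows, so a score taken at an early visit keeps its own date. In the 94.0% scenario, putting every unrecovered inpatient's last score on Day 23, with recoveries and deaths still dated to Day 28, gives about 98%. After Day 23 the risk set then holds only people who go on to recover or die. This is an extreme case, but it shows that zero bias requires scores dated Day 28 or later, not merely a visit within the window.

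**The case against.** The strongest answer is that the missing score should not arise. Protocol 6.5 schedules an ordinal review at Day 28 in addition to the dated changes, and both procedures tables mark it. The participants at issue are still in hospital, so the telephone option for discharged participants does not remove it. If it yields a score dated Day 28 for each of them, the bias is zero.

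A reader might therefore go too far in several directions:
- **That only changes are recorded after Day 14.** Not supported, because the Day 28 review is scheduled.
- **That the estimate is inflated even when protocol 6.5 is fully followed.** Not supported. With a score dated Day 28 for every unrecovered inpatient, the rule does no harm.
- **That every recovery leaves a dated record.** Too strong. SAP 6.2 recognises hospital exits that are neither discharge alive nor death, and a later recovery may then go unrecorded.
- **That a blank day after Day 14 means no change.** Not certain. A site that followed the table footnotes would have recorded neither persistence nor an in-hospital improvement.

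The review still cannot be relied on. The footnotes stop this data collection at Day 14 or discharge, SAP 6.2 provides for a missing Day 28 score, and 6.2.1 plans a status summary that leaves out days with missing scores.

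One could also read a carried-forward Day 28 status as non-missing, which would move censoring to Day 28. The SAP does not say so, and the reference in item 16 to an assessment date points the other way. That reading would also hold participants who left without being discharged alive at risk as unrecovered.

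The consequence is limited, too. SAP 6.2.1 already plans Day 28 percentages with 95% confidence intervals, and Day 28 status within each subgroup. Both use carried-forward status and keep unrecovered participants in the denominator, so a marked inflation could be seen by comparison.

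**Conclusion.** The point holds conditionally. As written, the rule can remove participants known to be in hospital and unrecovered from the risk set as early as Day 14, and so may inflate the competing-risk Day 28 estimates of recovery and improvement. The size depends on how many of them lack a score dated Day 28, which the documents do not give. It is zero if none do. In Illustration A (90.0% true) the excess is 2.1 points if half do and 7.5 if all do; in Illustration B (72.0% true) it is 5.1 and 18.0. The largest figures require that no unrecovered inpatient has any later score, contrary to the scheduled review. Part B is a single group with no formal testing (SAP 3.2, 3.3 and 3.5), so no test or error rate is affected. The change is worth making because two planned Day 28 results can otherwise disagree for no clinical reason, and it costs little.

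**What to change.** 1. In SAP 6.2.1 and Appendix 2 item 16, state that participants known to be hospitalized in the study without the event stay at risk to the earlier of Day 28 and the last date known in hospital. Keep censoring at the last score for withdrawal, or for a hospital discharge reason other than discharged alive.
2. State that a carried-forward status does not by itself set the censoring date.
3. Reconcile the footnotes in protocol Appendix 2 and SAP Appendix 1 with protocol 6.5 and SAP 3.8.2, and confirm that sites collected changes after Day 14. This comes first, because reading blank days as unchanged could miss in-hospital improvement at sites that stopped recording at Day 14.
4. Report how many unrecovered inpatients have no score dated Day 28 or later.

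The cost is a sentence or two in each of two places, one derivation and one count, with no new data collection. If all the Day 28 scores exist, the results should barely change.

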6.3. Changes from Protocol-Specified Efficacy Analyses

There are no changes from the protocol-specified efficacy analysis.

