8.1.4. Other Endpoints of Interest

Other endpoints of interest are:

- The proportion of participants with negative SARS-CoV-2 PCR
- Time to clinical improvement (days): clinical improvement is defined as a ≥ 2 -point improvement in clinical status (7-point ordinal scale) from Day 1
- Time to ≥ 1 -point improvement (days) from baseline clinical status
- Time to recovery: defined as an improvement in clinical status from a baseline score of 2 through 5 to a score of 6 or 7, or an improvement from a baseline score of 6 to a score of 7
- Time to modified recovery: defined as an improvement in clinical status from a baseline score of 2 through 4 to a score of 5, 6, or 7, or an improvement from a baseline score of 5 to a score of 6 or 7, or an improvement from a baseline score of 6 to a score of 7

- Time to room air: defined as an improvement in clinical status from a baseline score of 2 through 4 to a score of 5, 6, or 7
- Duration of oxygen therapy (days)
- Shift in oxygen support status from baseline
- Duration of hospitalization (days)
- All-cause mortality at Day 28

- The proportion of participants in the Extension Treatment Group with treatment emergent adverse events

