8.5.2. Secondary Analyses

The secondary endpoint of proportion of participants with treatment emergent AEs will be compared between each of the RDV groups and standard of care group in Part A using a Fisher's Exact test. The point estimates of the treatment differences and the associated 95% confidence intervals will be provided. Other endpoints of interest related to proportion of participants will be compared between treatment groups in Part A using a chi-square test or Fisher's Exact test. Efficacy endpoints that are measured as time to first event will be compared between treatment groups using a competing risk model (with death as the competing risk) and continuous endpoints will be compared between treatment groups using a Wilcoxon rank sum test or analysis of variance model.

The 7-point ordinal scale of clinical status and other efficacy endpoint of interest will be summarized descriptively for Part B.

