1. INTRODUCTION

This Phase 3 study is conducted in two parts. In Part A, approximately 600 participants who met all eligibility criteria were randomized in 1:1:1 ratio into one of the three treatment groups (2 remdesivir [RDV] regimens and 1 standard of care [SOC]). Part B starts after Part A is completed and includes up to approximately 1000 participants.

This statistical analysis plan (SAP) describes the statistical analysis methods and data presentations to be used in tables, figures, and listings (TFLs) for the analysis of Part B of Study GS-US-540-5774.

This SAP is based on the study protocol Amendment 2.0 dated 29 April 2020 and the electronic case report form (eCRF). The SAP will be finalized prior to data finalization. Any changes made after the finalization of the SAP will be documented in the clinical study report (CSR).

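### SAP 6.3 declares no efficacy changes, but the Part B plan omits time to room air and time to modified recovery and adds discharge alive to the ≥2-point improvement

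*SAP*

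**What the plan says.** - SAP 6.3, the section meant to disclose departures, reads in full: "There are no changes from the protocol-specified efficacy analysis".
- Protocol 8.5.2 sets the Part B requirement: "The 7-point ordinal scale of clinical status and other efficacy endpoint of interest will be summarized descriptively for Part B".
- Protocol 8.1.4 (repeated in 3.1) lists the other endpoints of interest. Three entries matter here. The virologic one is "The proportion of participants with negative SARS-CoV-2 PCR". The second is "Time to modified recovery: defined as an improvement in clinical status from a baseline score of 2 through 4"; any score of at least 5 qualifies, and further rules cover baselines 5 and 6. The third is "Time to room air: defined as an improvement in clinical status from a baseline score of 2 through 4 to a score of 5, 6"; discharge (score 7) qualifies as well.
- The same list defines clinical improvement as a gain of at least 2 points from Day 1, with no alternative criterion. SAP 6.2 defines it as a gain of at least 2 points in these terms: "improvement from baseline clinical status or discharged alive". The matching percentage endpoint in SAP 6.2 has the same addition, but SAP 6.2.1 calls the result simply ≥2-point improvement.
- The only SAP output for PCR results is a by-subject listing (SAP 7.3).

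**The concern.** A reader of the final report will rely on SAP 6.3 to learn whether the Part B efficacy results are those the protocol specified. If it says nothing changed, an endpoint that was dropped looks as though it never existed, and a widened endpoint is taken for the protocol's own. Part B has no hypothesis test, so its efficacy reporting rests on producing the prespecified descriptive endpoints under correct labels. Two things are at stake: protocol endpoints with no planned output, and an improvement percentage that can include 1-point changes under a 2-point label.

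**Working it through.** This is a comparison of texts. The inputs are the endpoint list in protocol 8.1.4, the Part B requirement in protocol 8.5.2, and SAP 6.2, 6.2.1, 7.3 and Appendix 2.

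**Step 1: endpoint count.** Leaving aside the adverse-event proportion for the Extension Treatment Group, the protocol lists 10 other endpoints of interest.

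| Protocol 8.1.4 | Part B SAP |
|---|---|
| Time to clinical improvement | Kept, definition widened |
| Time to ≥1-point improvement | Kept |
| Time to recovery | Kept |
| Duration of oxygen therapy | Kept, as days of oxygen support |
| Shift in oxygen support | Kept |
| Duration of hospitalization | Kept |
| All-cause mortality | Kept |
| Time to modified recovery | Absent |
| Time to room air | Absent |
| Proportion PCR negative | Listing only |

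Seven are kept: 10 − 7 = 3 have no summary. If PCR negativity is not counted as an efficacy endpoint, 2 of 9 are missing. The censoring rules in Appendix 2 (item 16) confirm the gap: they cover death, ≥2-point improvement, ≥1-point improvement and recovery only. No redaction mark appears in SAP 6.2 to 6.3 that would explain the absences.

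**Step 2: what omitting the two time-to-event endpoints loses.** Follow-up scores that count as an event:

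| Baseline | Modified recovery (protocol) | ≥1-point improvement (both) | Room air (protocol) |
|---|---|---|---|
| 2 | 5, 6, 7 | 3, 4, 5, 6, 7 | 5, 6, 7 |
| 3 | 5, 6, 7 | 4, 5, 6, 7 | 5, 6, 7 |
| 4 | 5, 6, 7 | 5, 6, 7 | 5, 6, 7 |
| 5 | 6, 7 | 6, 7 | not applicable |
| 6 | 7 | 7 | not applicable |

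Modified recovery and ≥1-point improvement coincide at baselines 4, 5 and 6 and differ only at 2 and 3. Room air applies only at baselines 2 to 4. At baseline 4 it is also the same event as a ≥1-point improvement. However, the planned ≥1-point analysis pools all baselines, and the subgroup displays named in SAP 6.2.1 cover only daily status and recovery. Time to room air therefore cannot be read from any planned output.

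**Step 3: the widened improvement definition.** Follow-up scores that count as improvement:

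| Baseline | Protocol: gain ≥2 | SAP: gain ≥2 or discharged alive (7) |
|---|---|---|
| 2 | 4, 5, 6, 7 | 4, 5, 6, 7 |
| 3 | 5, 6, 7 | 5, 6, 7 |
| 4 | 6, 7 | 6, 7 |
| 5 | 7 | 7 |
| 6 | none | 7 |

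For baselines 2 to 5, discharge is already a gain of at least 2 points (7 − 5 = 2), so the definitions agree. At baseline 6, discharge is a gain of 7 − 6 = 1. It is never an event under the protocol and always one under the SAP.

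**Step 4: size.** Let s be the share of treated Part B participants at baseline 6, and d the fraction of them discharged alive by the day in question. The SAP percentage exceeds the protocol percentage by s × d, which lies between 0 and s. The documents give neither quantity. To set the scale, assume the planned 1000 or so participants are all treated: every 10 who start at score 6 and go home add 10/1000 = 1 percentage point.

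**The case against.** The other side has a good deal of force on the size of the problem.

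- **Part B is descriptive.** It is single-arm, with no formal testing (SAP 3.3, 3.5), and the primary endpoint was analysed in Part A. No error rate or primary comparison depends on this. That stands.
- **Modified recovery is nearly redundant.** Inclusion requires SpO₂ above 94% on room air at screening, mechanical ventilation at screening is excluded, and the SAP's baseline oxygen categories are low-flow oxygen and room air only. Baselines 2 and 3 should be rare. That stands, but SAP 6.3 does not say so.
- **Movement to room air is still visible.** The oxygen-support shift table and daily status by baseline oxygen subgroup both show it. This is partly right: these are snapshots on set days, not the time-to-event endpoint. The SAP's own low-flow subgroup shows that it expects participants to whom the endpoint applies.
- **Baseline 6 should be rare, and the added clause is in plain sight.** Inclusion requires a need for medical care for COVID-19, whereas score 6 means that care is no longer needed. Rarity is likely. But stating the clause in SAP 6.2 does not make 6.3 accurate or repair the label in 6.2.1.

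A reader might also infer more than the documents support.

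- **That three efficacy endpoints are certainly missing.** Protocol 8.1.4 mixes types of endpoint and never calls PCR negativity an efficacy endpoint. Central swabs come only from a subset of participants at selected sites (protocol 6.6). The firm count is two.
- **That carrying forward the last known status breaks a protocol ban on imputation.** Protocol 8.3.2 says only that missing values are in general not imputed, and part of that section is redacted. SAP 6.2.1 also gives the daily status summary without days of missing score, and time-to-event endpoints are censored at the last observed score. This is not a demonstrated departure.
- **That the information in the omitted endpoints is wholly lost.** Step 2 shows otherwise for modified recovery.

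**Conclusion.** The no-changes statement in SAP 6.3 is wrong as written. At least two protocol efficacy endpoints have no planned Part B output, and one retained endpoint has been widened without being declared. The practical loss is mainly time to room air at baselines 2 to 4. For modified recovery, the loss is confined to baselines 2 and 3. The change to clinical improvement affects baseline 6 only and adds at most the share of participants who start there; that share is not given and is probably small. PCR negativity is an arguable third omission.

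This should be corrected, but it is a matter of faithful reporting rather than a threat to the trial's conclusions. Part A's primary analysis is not affected. Two assumptions apply: that the protocol supplied is the Amendment 2.0 on which SAP section 1 says it is based, and that the reference in protocol 8.5.2 to other efficacy endpoints covers those derived from the ordinal scale, since it exempts none of them.

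**What to change.** 1. Add time to room air (baselines 2 to 4) and time to modified recovery to SAP 6.2 and 6.2.1, using the competing-risk code and censoring rule already in Appendix 2. Alternatively, for modified recovery, state in 6.3 that the ≥1-point improvement covers it for baselines 4 to 6. If so, also name time to ≥1-point improvement in the competing-risk sentence of 6.2.1, which at present mentions only clinical improvement and recovery.
2. Report ≥2-point improvement by the protocol definition beside the SAP version, or label the SAP version everywhere as ≥2-point improvement or discharged alive. Give the number of participants at baseline 6.
3. Summarize the proportion PCR negative where data exist, with its denominator and the Clopper-Pearson interval already specified, or list its omission with a reason.
4. Replace the sentence in 6.3 with the list of actual departures and the reason for each.

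The cost is a few extra tables from ordinal data already collected, plus SAP wording. No new data collection is needed; the PCR summary would be limited to participants with results.
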